# **2 PARTICIPANTS**

**2.1** Participants. Describe the general characteristics of the subject populations or groups, including age range, gender, health status, and any other relevant characteristics.

The initial IRB application is for Phase 1 activities only. Modifications will be submitted when appropriate for Phase 2 and 3 procedures.

Phase 1

Phase 1 data analysis (100,000) participants will be consumers who are seeking services from Mental Health America (MHA) and Talkspace (TS). MHA and TS offer services in both English and Spanish, thus we will include both English and Spanish speakers. English and Spanish speaking MHA consumers will be identified as such based on the language in which they choose to interact with the website (e.g. taking an English language or Spanish language screen). For TS consumers, previous data analysis shows that 99.5% of services are provided in English. If services are provided in Spanish, this information is available via the site's meta-data and will be noted in the dataset. Participants will be largely female, representative of the US population and who have screened positive to any mental health problem. While we anticipate that most participants will be 14 and older, MHA consumers may be as young as 6. We anticipate that most will be suffering from depression or anxiety.

Phase 1 focus group participants will be randomly chosen from MHA and TS English speaking consumers aged 18 and over.

During Phase 1, Talkspace will invite consumers to complete a survey about communications from Talkspace. These survey respondents will be English speaking, TS consumers aged 18 and over who choose to respond to invitations received in-app, by email, or as a push notification.

## Phase 2

Phase 2 micro-randomized trial (MRT) participants will be the same as Phase 1 participants: consumers seeking services from MHA and TS, including both English and Spanish speakers with no exclusion criteria around age, gender, clinical presentation or other attribute.

Phase 2 focus group participants will be English speaking MHA and TS consumers aged 18 and over.

Phase 3b: Participants for data collection of Study 1, (SMART trial) will be consumers seeking services from MHA who have chosen to start the PHQ-9 mental health test in English on the MHA platform. They will include those who can read English, with no exclusion criteria around age, gender, or clinical presentation or other attributes.

The inclusion/exclusion criteria for Study 2 (the survey data collection on 250 participants) will be more selective. These participants will be consumers seeking services from MHA, and more specifically those who based on either of these screeners have identified as experiencing at least moderate symptoms of depression and/or anxiety. Participants will be 18 and older with little to no experience with the concept of cognitive reframing.

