- 2. Ability to create DMH engagement subgroups using data currently collected by MHA and TS. Both MHA and TS currently collect a considerable amount of objective and subjective information from their consumers regarding their demographics, symptom severity, goals for seeking care, and their use of services. Demographically, the two organizations serve similar populations. At MHA, consumers are primarily a helpseeking population with higher percentages of low-income individuals (over 50% report household income below \$40,000 a year), who are at risk for mental health conditions (74% of screeners score "positive" or above criteria of concern), and have never been treated for their condition (65% of those who screen positive report having no current or past mental health diagnosis). TS consumers are also primarily first-time treatment seekers (60% report no prior mental health treatment) and most report symptoms at baselines that indicate risk for a mental health condition (70% score above clinical thresholds). Whether paying out of pocket or using insurance, TS users tend to be middle-higher income individuals and 75% report a Bachelors' degree or higher. Information on service use differs between MHA and TS because of the differences in their platforms and DMH offerings. MHA service use is defined by the use of self-help tools, use of services MHA recommends (including therapeutic video games, forums and linkages to Talkspace), and time using MHA created tools. Self-reported tools at MHA include screeners, reasons for searching, and satisfaction with tools offered and used. TS service use is defined by number of texts sent, time between texts, use of educational materials TS creates, completion of self-rating scales, and text content. Self-report measures collected by TS include measures of working alliance, treatment satisfaction and an exit interview at time of termination. See Table 1 for full details. The wealth of data available for analysis will allow us to create rich, informative engagement clusters that will inform future subgroups for Aim 2 and to be tested in Aim 3.

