analyses on over 10,000 TS consumers to identify engagement patterns that determine initial predictors of DMH engagement. TS collected the PHQ-9 on consumers every 3 weeks. Completion of these measures is a good indicator of clinical engagement in treatment. Results indicated engagement was a function of plan type and symptom severity. Of the three plan types, weekly video chat had the largest early disengagement, with only 17% of those enrolled engaged longer that 6 weeks (fig 2a). 40% of consumers initiate treatment but do not engage for 3 weeks, 21% do not engage longer than 6 weeks and another 12% do not engage past 9 weeks. Only 2% engage for a full year (fig 2). Consumers who exhibit more symptoms at intake assessment are less likely to disengage from treatment, with the odds of disengagement decreasing by 3.3% for each additional point on intake PHQ-9. However, higher symptoms over the course of care results in greater disengagement, with the odds of disengagement increasing by 5.3% for each additional point on the final PHQ-9 assessment completed. Both MHA and TS are highly motivated to understand engagement and the impact engagement has on clinical outcomes.

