## **Screens & Surveys**

Both MHA and TS collect information from consumers about their demographics such as age, gender, marital status, race/ethnicity, income status and education. MHA and TS also collects these symptom measures at initial engagement with services:

• PHQ9 (depression),

- GAD7 (anxiety),
- Prodromal Questionnaire-Brief Version (PQ-B; psychosis);
- Brief Bipolar Test;
- SWED (eating disorders),
- PC-PTSD (PTSD),
- CAGE-AID (Substance Use Disorder);
- Work Health Survey,
- caregiver status, and the
- Duke Social Support Scale, a measure of perceived social support.

These variables will be used to characterize consumers, and may serve as moderators of engagement (Aims 1, 2 and 3a) and clinical outcomes (Aim 3b). These measures have been uploaded to Zipline.

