## Phase 3:

Study 1 (SMART): We will use a Sequential Multiple Random Assignment Trial (SMART) with an expected 50,000 users, with the goal of optimizing engagement strategies so that web users engage with MHA resources most relevant to their needs, including psychoeducation, links to treatment providers, or self-help tools. Participants will be randomized to type of screening results language, with conditions including results-as-usual, or tailoring by: 1) demographics (race, LGBTQ status, age) or 2) mental health severity (screening results) & perceived need. Subsequent randomization will determine whether single-item self-help tools embedded in content pages serve to engage users in active mental health strategies. Participants will be MHA consumers who land on the PHQ-9 mental health test page on the MHA website.

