ENHANCING ENGAGEMENT WITH DIGITAL MENTAL HEALTH CARE

STUDY00010958

07/03/2024

NCT04507360

Aim 3B Statistical Analysis Plan. For Study 1, all research questions were examined via logistic regressions. We assessed whether participants' first condition (i.e., demographics survey or Next Steps survey) predicted the odds of disengagement. Within participants who completed the demographics survey, we examined whether the odds of disengaging and clicking a featured resource on the screening results page significantly differed for participants in the Tailored Resources to Demographics condition compared to control (i.e., Generic Response + Generic Resources). Within participants from the Next Steps survey condition, we tested whether engagement significantly differed for participants shown Tailored Response + Generic Resources, Generic Response + Tailored Resources to Desired Resources, and Tailored Response + Tailored Resources to Desired Resources compared to control. We aimed to identify the optimal tailoring strategy by comparing engagement across all tailoring conditions, with Tailored Resources to Demographics set as the reference group. For Study 2, research questions were examined via t-tests and Cohen's d effect sizes comparing engagement, short-term restructuring effectiveness, longer-term effectiveness (e.g., skill acquisition, reductions in depression and anxiety), and heterogeneous treatment effects by condition (i.e., control, DIY tool without AI, and DIY tool with AI).

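### Study 1 chooses its best results page from effects pooled over all PHQ-9 scores; page effects by severity should be reported beside the pooled effect

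*Protocol*

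**What the plan says.** Protocol section 2.1 defines Study 1 participants as MHA users "who have chosen to start the PHQ-9 mental health test in English on the MHA platform", "with no exclusion criteria around age, gender, or clinical presentation or other attributes". Section 5.1 (Phase 3, Study 1) plans the trial "with an expected 50,000 users", "with the goal of optimizing engagement strategies so that web users engage with MHA resources most relevant to their needs". The same paragraph makes severity, as shown by the screening result, together with perceived need, one basis for tailoring the results language. Section 5.4 says that the PHQ-9 is collected at initial engagement in Study 1.

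The SAP analyses every Study 1 question by logistic regression. In the demographics-survey branch it "examined whether the odds of disengaging and clicking a featured resource on the screening results page significantly differed" between the tailored page and control. In the Next Steps branch it compares three tailored pages with control on engagement, which it does not define. It then compares engagement across all tailoring conditions to find the best strategy. No PHQ-9 term, stratum or interaction is named for any of these. For Study 2 the same SAP does list heterogeneous treatment effects.

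**The concern.** The stated goal is engagement that fits need, and severity is one of the things being tailored on. A contrast averaged over severity answers a different question: which page moves the average test-taker. Two quite different pages can give the same pooled odds ratio. One mainly keeps people with few symptoms on the site; the other helps people who screen positive. If the first has a large enough effect in its stratum it will rank first, and the SAP as written would not reveal this. A benefit confined to symptomatic users is also diluted in the pooled test.

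The results page reports the screening result, so the score exists before the page is seen and the page cannot alter it. It is therefore a legitimate baseline variable for the results-page contrasts.

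**Working it through.** The documents give no power basis, disengagement rate, allocation ratio or severity-specific effect for Study 1, so there is no planned figure to reproduce. What follows is illustration.

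**Inputs**
- Share screening negative: section 1.8b describes MHA consumers "who are at risk for mental health conditions (74% of screeners score" positive, so about 26% are negative. This covers all MHA screens, not the PHQ-9 alone. Range used: 20% to 35%.
- Users: 50,000. Assumed: equal splits and everyone reaching a results page. That gives 25,000/4 = 6,250 per Next Steps page and 25,000/2 = 12,500 per demographics-branch page.
- Rate of leaving: assumed 50%, 68% or 91%. The last two are the historic bounce rates in section 1.8b, item 5.
- Two-sided 5% test.

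**1. When the ranking reverses.** Pooled effect = 0.26 × (effect in negatives) + 0.74 × (effect in positives). A negatives-only page outranks a positives-only page when its effect is more than 0.74/0.26 = 2.85 times as large. With 20% negative the ratio is 0.80/0.20 = 4.0; with 35% it is 0.65/0.35 = 1.9.

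**2. An example (68% base, 6,250 per page).**
- Page A cuts leaving by 10 points in negatives and by nothing in positives: 68 − 0.26 × 10 = 65.4% pooled. Power against control is 87%.
- Page B cuts leaving by 2 points in positives only: 68 − 0.74 × 2 = 66.5%. Power is 42%.
- Page A would rank first although it does nothing for screen-positives.

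**3. How often a negatives-only page would be significant (50% base).** The standard error of a difference is √(2 × 0.25/n): 0.894 points at n = 6,250 and 0.632 at n = 12,500. Effects of 6 and 10 points in negatives become 1.56 and 2.6 points pooled.
- Next Steps pages: z = 1.74 and 2.91, power 41% and 83%.
- Demographics-branch pages: z = 2.47 and 4.11, power 69% and 98%.
- If only half of users reach a Next Steps page (n = 3,125, standard error 1.265): z = 1.23 and 2.06, power 23% and 54%.

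**4. Dilution of a positives-only benefit.** The pooled z scales with 0.74 and the within-stratum z with √0.74 = 0.86. The ratio is 1.16, equivalent to 1.16² = 1.35 times as many users.

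**5. Whether stratified estimates are affordable.** Smallest difference detectable with 80% power at 6,250 per page and a 68% base:
- pooled: 2.36 points
- positives (0.74 × 6,250 = 4,625 per page): 2.75 points
- negatives (1,625 per page): 4.67 points

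If only a quarter of users reach the page, the pooled value is 4.76 points and the positive-stratum value 5.55.

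**6. The interaction test.** At a 50% base its standard error is √(0.5/4,625 + 0.5/1,625) = 2.04 points, so 80% power needs a difference between strata of about 2.8 × 2.04 = 5.7 points. It is much weaker than the stratum estimates, so reporting them should not depend on its significance.

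**7. Chance imbalance.** The standard deviation of the between-page difference in negative share is √(2 × 0.26 × 0.74/6,250) = 0.8 points, which is trivial.

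**The case against.** The best defence is that the average effect over all test-takers is a coherent target for a page that every visitor sees, and that admitting all scores was deliberate. In the scenarios above the pooled effect is real, so a significant result is a correct one. Section 5.4 measures need by stated intention and a perceived-need question, not by a PHQ-9 cut-off, so a low scorer who reads on may be a success. All of this stands, and it is why the pooled effect should remain the main analysis.

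Several stronger readings are tempting but not supported:
- *Severity is ignored in Study 1.* Section 5.1 uses it for tailoring; it is absent only from the SAP's models.
- *Leaving counts as failure for everyone.* The SAP does not say this, and it also tests clicking a featured resource, though that too is pooled.
- *Severity confounds the comparison.* Pages are randomized.
- *The protocol shows that page effects vary with severity.* The preliminary result, "with the odds of disengagement decreasing by 3.3% for each additional point on intake PHQ-9", comes from Talkspace therapy clients followed over weeks. It is prognostic, and the same paragraph reports the opposite direction for the final PHQ-9.
- *The protocol rules out moderators for Study 1.* The statement that symptom measures "may serve as moderators of engagement (Aims 1, 2 and 3a) and clinical outcomes (Aim 3b") is permissive and sits in the Phase 1 procedures. It neither excludes nor supplies such an analysis.
- *The choice of best page should rest on users scoring 10 or more.* That cut-off is Study 2 eligibility, on the PHQ or GAD. Moving the conclusion there would change the target population, and the SAP, dated 07/03/2024, is already in the past tense.

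**Conclusion.** The gap is real but limited. The SAP pools over severity when it compares results pages and picks the best one, in a design that tailors on severity, aims at fit to need and collects the score. The pooled analysis is unbiased for all comers; it cannot say whether the chosen page works in symptomatic users. A wrong ranking for those users needs an effect in screen-negatives about 2.85 times that of a competing positives-only page (1.9 to 4.0 times for 35% to 20% negative), so it is possible but not to be presumed. The power figures rest on constructed effects, equal allocation and full reach, and fall considerably if fewer users get to the page. The 26% is a proxy and need not match the share scoring below 10 on the PHQ-9. This is an inexpensive improvement to the analysis and does not invalidate the trial.

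**What to change.** - In each results-page regression, for disengagement and for featured-resource clicks, add PHQ-9 severity as a baseline covariate and a page-by-severity term.
- Report page effects by severity stratum (for example 10 or more versus below 10) beside the pooled effect, whether or not the interaction is significant.
- Keep the pooled all-comer effect as the main analysis. State whether the page named best is consistent across strata.
- Label the stratified results exploratory, or post hoc if outcomes were known when they were added.
- Do not adjust the first-stage survey contrast for PHQ-9 unless the score was complete before that assignment. Users enter on starting the test, so the score may be missing for those who leave early.
- Be cautious with PHQ-9 adjustment in the comparison across all tailoring conditions. It crosses the two survey branches, and the survey may have influenced who finished the PHQ-9.

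The cost is a few sentences in the SAP and some model terms on data already collected. The downsides are wider intervals within strata, mainly in the smaller one, and a few more contrasts to interpret.

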# (2.2) Inclusion and exclusion criteria.

**a. Inclusion criteria.** Describe the specific criteria that will be used to decide who will be included in the research from among interested or potential subjects. Define any technical terms in lay language.

#### Phase 1

Phase 1 data analysis activities: Consumers seeking services from MHA and TS, English and/or Spanish speaking

Phase 1 Focus Group participants will be randomly chosen from MHA and TS English speaking consumers aged 18 and over

Phase 1 Talkspace Survey: English speaking TS consumers, aged 18 and over

#### Phase 2

Phase 2 micro-randomized trials (MRTs): Consumers seeking services from MHA and TS, English and/or Spanish speaking

Phase 2 focus groups: MHA and TS consumers aged 18 and over

• Talkspace only: Focus groups launching in November 2022 will focus on users' thoughts and reactions to receiving nudges (e.g., push notifications, emails) and their impact on engagement with the platform. For these focus groups only, inclusion criteria will be TS consumers aged 18 and over who have used Talkspace messaging-based therapy in the past 3 months, and have the Talkspace mobile app installed on their mobile device

## Phase 3

Phase 3b Study 1 SMART trial participants will be consumers seeking to take a mental health test from MHA and able to read English

Phase 3b Study 2 longitudinal survey participants will be consumers who have completed an English PHQ or GAD test from MHA and scored greater than or equal to 10 either of the measures. They will be 18 years or older, residing in the United States and who indicate that they have little or no familiarity with the concept of cognitive reframing.

**b. Exclusion criteria.** Describe the specific criteria that will be used to decide who will be excluded from the research from subjects who meet the inclusion criteria listed above. Define any technical terms in lay language.

#### Phase 1

Phase 1 data analysis activities: Non-English or Spanish speaking

Phase 1 Focus Group participants: non-English speaking, younger than 18

Phase 1 Talkspace Survey: Non-English speaking, younger than 18

## Phase 2

Phase 2 MRTs: non-English or Spanish speaking consumers

Phase 2 Focus Groups: non-English speaking, younger than 18

Talkspace only: Focus groups launching in November 2022 will focus on users' thoughts and reactions to receiving nudges (e.g., push notifications, emails) and their impact on engagement with the platform. For these focus groups only, exclusion criteria will be TS users younger than 18, and/or have not used TS messaging-based therapy in the past 3 months (e.g., have only used non-messaging based TS services such as video based services, couples counseling, or psychiatry services), and/or do not have the TS mobile app downloaded on their mobile device


 
No
 
Yes → If yes, if a subject becomes a prisoner while participating in the study, will any study procedures and/or data collection related to the subject be continued while the subject is a prisoner?
 
No
 

Yes → If yes, describe the procedures and/or data collection that will continue with prisoner subjects
p. 150.15. 55.5,55.15

**2.4**) **Protected populations**. IRB approval is required for the use of the subject populations listed here. Check the boxes for any of these populations that will be purposefully included. (In other words, being a part of the population is an inclusion criterion for the study.)

The WORKSHEETS describe the criteria for approval but do not need to be completed and should not be submitted.

Population	Worksheet	
Fetuses in utero	WORKSHEET Pregnant Women	
Neonates of uncertain viability	WORKSHEET Neonates	
Non-viable neonates	WORKSHEET Neonates	
Pregnant women	WORKSHEET Pregnant Women	
a. If you check any of the boxes above, use this space to provide any information that may be relevant for the IRB to consider.		

**2.5** Native Americans or non-U.S. indigenous populations. Will Native American or non-U.S. indigenous populations be actively recruited through a tribe, tribe-focused organization, or similar community-based organization?

Indigenous people are defined in international or national legislation as having a set of specific rights based on their historical ties to a particular territory and their cultural or historical distinctiveness from other populations that are often politically dominant.

Examples: a reservation school or health clinic; recruiting during a tribal community gathering

X No Yes

→ If yes, name the tribe, tribal-focused organization, or similar community-based organization. The UW IRB expects that tribal/indigenous approval will be obtained before beginning the research. This may or may not involve approval from a tribal IRB. The study team and any collaborators/investigators are also responsible for identifying any tribal laws that may affect the research.

**(2.6) Third party subjects.** Will the research collect private identifiable information about *other individuals* from the study subjects? Common examples include: collecting medical history information or contact information about family members, friends, co-workers.

"Identifiable" means any direct or indirect identifier that, alone or in combination, would allow you or another member of the research team to readily identify the person. For example, suppose that the research is about immigration history. If subjects are asked questions about their grandparents but are not asked for names or other information that would allow easy identification of the grandparents, then private identifiable information is not being collected about the grandparents and the grandparents are not subjects.

APPLICATION IRB Protocol

X	No
---	----

Yes	→ If yes, these individuals are considered human subjects in the study. Describe them and what data will be collected about them.

**2.7 Number of subjects.** Is it possible to predict or describe the maximum number of subjects (or subject units) needed to complete the study, for each subject group?

Subject units mean units within a group. For most research studies, a group will consist of individuals. However, the unit of interest in some research is not the individual. Examples:

- Dyads such as caregiver-and-Alzheimer's patient, or parent and child
- Families
- Other units, such as student-parent-teacher

Subject group means categories of subjects that are meaningful for the specific study. Some research has only one subject group – for example, all UW students taking Introductory Psychology. Some common ways in which subjects are grouped include:

- By intervention for example, an intervention group and a control group.
- By subject population or setting for example, urban versus rural families
- By age for example, children who are 6, 10, or 14 years old.

The IRB reviews the number of subjects in the context of risks and benefits. Unless otherwise specified, if the IRB determines that the research involves no more than minimal risk: there are no restrictions on the total number of subjects that may be enrolled. If the research involves more than minimal risk: The number of enrolled subjects must be limited to the number described in this application. If it is necessary later to increase the number of subjects, submit a Modification. Exceeding the IRB-approved number (over-enrollment) will be considered non-compliance.

No → If no, provide the rationale in the box below. Also, provide any other available information about the scope/size of the research. You do not need to complete the table.

Example: It may not be possible to predict the number of subjects who will complete an online survey advertised through Craigslist, but you can state that the survey will be posted for two weeks and the number who respond is the number who will be in the study.

Yes → If yes, for each subject group, use the table below to provide the estimate of the maximum desired number of individuals (or other subject unit, such as families) who will complete the research.

Group name/description	Maximum desired number of individuals (or other subject unit, such as families) who will complete the research  Provide numbers for the site(s) reviewed by the UW IRB and for the study-wide total number; example: 20/100
Phase 1: Data Analysis Activities	100,000
Phase 1: Focus Groups	48
Phase 1: Talkspace Survey	Approx 500
Phase 2: Micro-randomized Trials (MRTs)	50,000
Phase 2: Focus Groups	48

APPLICATION IRB Protocol

Document Date & Version 06/26/2020

Phase 3: SMART Study 1	50,000
Phase 3: Longitudinal Surveys Study 2	300

**2.8 COVID-19 Screening**. If there will be any in-person interactions with the subjects, describe how you will screen them for COVID-19 symptoms within the 24 hours before the interaction. Also, describe the COVID-19 screening procedures for the study staff who will interact with the subjects.

Acceptable procedures include some type of symptom check or attestation, or a SARS-CoV-2 test with quick access to results. Symptom attestation involves an individual reviewing a list of symptoms and declaring the presence or absence of those symptoms. HSD strongly encourages adapting this Washington State Department of Health Screening Tool https://www.doh.wa.gov/Portals/1/Documents/1600/coronavirus/Employervisitorscreeningquidance.pdf or the UW EH&S Example Symptom Self-Attestation in this document:

https://www.ehs.washington.edu/system/files/resources/guidance-symptom-monitoring-COVID-19.pdf. If you will test for the virus, you must also describe here whether the testing lab is CLIA-certified and how the results will be reported to the subjects.

N/A – all procedures are remote

